4.1.2.3. ABPM

The ABPM device will be attached to the nondominant arm and participants will be instructed to wear the monitor for a 24- to 27-hour period. Participants will be instructed to keep track of daily activities throughout the testing period and not to engage in strenuous activity.

Ambulatory BP measurements

- should be collected on a typical workday, not on a non-working day
- will be recorded every 30 minutes during daytime hours (0700 to 2200 hours), and
- will be recorded every 60 minutes during nighttime hours (2200 to 0700 hours).

A 24-hour session of ambulatory monitoring produces technically acceptable measurements if $\geq 70\%$ of the readings are valid. Between Visit 3 and Visit 4 (Week 0) and within 7 days following Visit 11 (Week 24) and Visit 14 (Week 36), participants will undergo a 24-hour ambulatory monitoring session. Upon return of the ABPM device, the recordings must be transmitted to the Core Laboratory and reviewed for validity of the readings before the participant leaves the site. If a technically satisfactory result is not achieved (less than 70% of readings are valid), the investigator should review the device settings and placement and the participant's activity track to correct any user error or device malfunctions. Another 24-hour ambulatory monitoring session should be conducted prior to Visit 4 (Randomization) or within 14 days following Visit 11 and Visit 14, respectively. If the second session also provides technically unsatisfactory results, data will be considered missing and the participant may continue in the study.

4.2. Scientific Rationale for Study Design

Data from the Phase 1 program in patients with T2D demonstrated that LY3437943 has the potential to induce clinically meaningful weight loss (that is, 5%-10% or more) with a safety profile consistent with other GLP-1 and GIP/GLP-1RAs.

The placebo arm is included to determine whether any efficacy or safety effects of LY3437943 are different in magnitude from no treatment (that is, placebo). Although it will not be feasible to blind the participant and the investigator to the injection volume of study drug, they will not know whether the participant is receiving LY3437943 or placebo. To preserve the blind, participants randomized to placebo will be randomly assigned to follow the injection dose schedule for 1 of the LY3437943 treatment arms.

Consistent with current guidelines for weight management, all participants will receive diet and physical activity counseling throughout the study, which will be based on guidelines published by the U.S. Department of Agriculture and U.S. Department of Health and Human Services (HHS 2018; USDA and HHS 2020).

The primary efficacy measure, mean percent change in body weight, is an accepted Phase 2 endpoint for investigational drugs being developed for weight management (FDA 2007). In addition, the protocol includes other parameters relevant to assessment of the effects of LY3437943 on safety, BP, HR, lipids, glycemic control, mechanism of action, PK parameters, and patient-reported outcomes.

The primary objective will be evaluated at 24 weeks because this period is considered adequate for evaluation of weight loss efficacy in a Phase 2 trial and sufficient to assess the dose–exposure–response of LY3437943 efficacy for selection of doses to be included in Phase 3 testing. The planned 48-week treatment period should be sufficient to capture the maximal or near-maximal weight loss effects of LY3437943. The putative mechanism of action of LY3437943 suggests that treatment with LY3437943 will result in continued weight loss over

this treatment period. In addition, safety and tolerability over a wide dose range of LY3437943 versus placebo will be assessed to enable robust benefit–risk characterizations in treatment of participants who have obesity or are overweight.

LY3437943 was well tolerated up to a 3 mg dose in the single ascending dose study (Study GZBA) and up to a 12 mg dose with gradual dose escalation in the multiple ascending dose study (Study GZBB). Therefore, the highest dose in this study will be 12 mg. In addition, 2 dose escalation schemes, starting with either 2 mg or 4 mg doses, are designed to provide information on optimal dose escalation schemes for Phase 3 clinical development.

To minimize the potential confounding effect of changes to concomitant medications, participants will be permitted to use concomitant medications that do not interfere with the assessment of efficacy or safety characteristics of the study treatments.

The sample size is determined based on data from Study GZBB that provided preliminary PD data for LY3437943 in participants with T2D over a 12-week treatment period, and on data from the semaglutide Phase 2 obesity study (O’Neil et al. 2018).

4.3. Justification for Dose

LY3437943 doses of 1, 4, 8, and 12 mg, administered subcutaneously QW, were selected based on the following

- Safety and tolerability of LY3437943 in healthy participants and participants with T2D in the Phase 1 studies GZBA (0.1 to 6 mg dose range) and GZBB (0.5 to 12 mg dose range).
- PK/PD modeling of preliminary data from Study GZBB.
- Acceptable margin of safety for the 12-mg maximum dose in this study relative to the no-observed-adverse-effect level in rats and monkeys in the 6-month toxicology studies.
- A maintenance dosage of 1 mg is predicted to achieve LY3437943 concentration levels that will demonstrate greater body weight loss compared with placebo and is being investigated in this study to enable full characterization of exposure–response relationships.
- Maintenance dosages of 4, 8, and 12 mg are expected to provide clinically relevant weight loss relative to placebo with increasing weight loss with increasing dose. For these doses, a starting dose of 2 or 4 mg prior to dose escalation will be investigated to evaluate the impact on tolerability and safety findings.
- The selected dose levels and dose range will support a robust dose–exposure–response analysis of multiple safety and efficacy measures to support selection of dose(s) of LY3437943 with optimal benefit/risk ratio for further clinical development.

4.4. End of Study Definition

A participant is considered to have completed the study if he or she has completed all required phases of the study including the last visit or the last scheduled procedure shown in the SoA.

The end of the study is defined as the date of the last visit of the last participant in the study or last scheduled procedure shown in the SoA for the last participant in the trial globally.

5. Study Population

Prospective approval of protocol deviations to recruitment and enrollment criteria, also known as protocol waivers or exemptions, is not permitted.

5.1. Inclusion Criteria

Participants are eligible to be included in the study only if all the following criteria apply:

Age

1. Participant must be 18 to 75 years of age inclusive, at the time of signing the informed consent.

Type of Participant and Disease Characteristics

2. Have a BMI of
 - $\geq 30 \text{ kg/m}^2$ and $\leq 50 \text{ kg/m}^2$
 - $\geq 27 \text{ kg/m}^2$ and $< 30 \text{ kg/m}^2$ with at least 1 of the following weight-related comorbidities
 - hypertension: on BP-lowering medication or having systolic BP ≥ 130 mmHg or diastolic BP ≥ 80 mmHg at screening
 - dyslipidemia: on lipid-lowering medication or having low-density lipoprotein (LDL) ≥ 160 mg/dL (4.1 mmol/L) or triglycerides ≥ 150 mg/dL (1.7 mmol/L), or high-density lipoprotein (HDL) < 40 mg/dL (1.0 mmol/L) for men or HDL < 50 mg/dL (1.3 mmol/L) for women at screening
 - cardiovascular disease: (for example, ischemic cardiovascular disease, New York Heart Association [NYHA] Functional Classification Class I-II heart failure)
3. In the investigator's opinion, are well motivated, capable, and willing to
 - learn how to self-inject study drug, as required for this protocol (visually impaired persons who are not able to perform the injections must have the assistance of a sighted individual trained to inject the study drug; persons with physical limitations who are not able to perform the injections must have the assistance of an individual trained to inject the study drug)
 - inject study drug (or receive an injection from a trained individual if visually impaired or with physical limitations), and
 - follow study procedures for the duration of the study, including, but not limited to, follow lifestyle advice (for example, dietary changes and physical activity plan), maintain a study drug administration log, and complete required questionnaires.

In addition, a subgroup of approximately 100-125 participants will meet the following inclusion criterion

4. Have liver fat content $\geq 10\%$ by MRI-PDF

Sex

5. Male and/or female

Contraceptive use by men or women should be consistent with local regulations regarding the methods of contraception for those participating in clinical studies.

Males, women of childbearing potential and women not of childbearing potential (for definitions, see Section 10.5 [Appendix 5]) can participate in this study considering the following:

- males agree to refrain from sperm donation and to use contraceptive methods as described in Section 10.5 (Appendix 5) throughout the study and for 5 half-lives of study drug plus 90 days, corresponding to 4 months after the last injection.
- women of childbearing potential must have negative pregnancy tests at Visit 1 and Visit 4 as indicated in the SoA and agree to use contraceptive methods as described in Section 10.5 (Appendix 5) throughout the study and for 5 half-lives of study drug plus 30 days, corresponding to 2 months after the last injection. Female participants should not be breastfeeding.

Note: Hormone replacement therapy in postmenopausal women and contraceptives containing an estrogen and a progestin (oral or transdermal system) in premenopausal women are allowed but women must be on stable therapy for 3 months prior to screening.

Informed Consent

6. Capable of giving signed informed consent as described in Section 10.1 (Appendix 1), which includes compliance with the requirements and restrictions listed in the ICF and in this protocol.

5.2. Exclusion Criteria

Participants are excluded from the study if any of the following criteria apply:

Medical Conditions***Diabetes Related***

7. Have history of diabetes mellitus including T1D or T2D, history of ketoacidosis, or hyperosmolar state/coma
8. Have at least 1 laboratory value suggestive of diabetes during screening, including 1 or more of HbA1c $\geq 6.5\%$ (48 mmol/mol), fasting serum glucose ≥ 126 mg/dL (7.0 mmol/L), or random glucose ≥ 200 mg/dL (11.1 mmol/L)

Obesity Related

9. Have a self-reported change (increase or decrease) in body weight >5 kg within 3 months prior to screening
10. Have a prior or planned surgical treatment for obesity (excluding liposuction or abdominoplasty, if performed >1 year prior to screening)

11. Have or plan to have endoscopic and/or device-based therapy for obesity or have had device removal within the last 6 months prior to screening including but not limited to
 - mucosal ablation
 - gastric artery embolization
 - intragastric balloon, and
 - duodenal-jejunal endoluminal liner

Other Medical

12. Have renal impairment measured as estimated glomerular filtration rate (eGFR) <45 mL/min/1.73 m², calculated by Chronic Kidney Disease-Epidemiology (CKD-EPI) as determined by central laboratory during screening
13. Have a known clinically significant gastric emptying abnormality (for example, severe gastroparesis or gastric outlet obstruction) or chronically take drugs that directly affect GI motility
14. Have a history of acute or chronic pancreatitis. A participant with a history of acute pancreatitis caused by gallstones may be included in the study if the participant has a cholecystectomy to resolve the problem
15. Have thyroid-stimulating hormone outside of the range of 0.4 to 6.0 mIU/L at screening visit

Note: Participants receiving treatment for hypothyroidism may be included, provided their thyroid hormone replacement dose has been stable for at least 6 months.

Note: Thyroid-stimulating hormone values above the normal range can, in some participant, suggest subclinical hypothyroidism. If, in the investigator's opinion, the participant has subclinical hypothyroidism and may require initiation of thyroid hormone replacement during the study, the participant should be excluded from the study.

16. Have obesity induced by other endocrinologic disorders (for example, Cushing's syndrome) or diagnosed monogenetic or syndromic forms of obesity (for example, Melanocortin 4 Receptor deficiency or Prader-Willi Syndrome)
 17. Have a history of significant active or unstable Major Depressive Disorder (MDD) or other severe psychiatric disorder (for example, schizophrenia, bipolar disorder, or other serious mood or anxiety disorder) within the last 2 years
- Note:*** Participants with MDD or generalized anxiety disorder whose disease state is considered stable for the past 2 years and expected to remain stable throughout the course of the study, in the opinion of the investigator, may be considered for inclusion if they are not on excluded medications

18. Have a lifetime history of suicide attempt
19. Have a Patient Health Questionnaire-9 (PHQ-9) score of 15 or more at Visit 1

20. On the C-SSRS at Visits 1, 3, or 4, prior to randomization:
- a “yes” answer to Question 4 (Active Suicidal Ideation with Some Intent to Act, Without Specific Plan) on the “Suicidal Ideation” portion of the C-SSRS
 - or**
 - a “yes” answer to Question 5 (Active Suicidal Ideation with Specific Plan and Intent) on the “Suicidal Ideation” portion of the C-SSRS
 - or**
 - a “yes” answer to any of the suicide-related behaviors (actual attempt, interrupted attempt, aborted attempt, preparatory act, or behavior) on the “Suicidal Behavior” portion of the C-SSRS
- and**
- the ideation or behavior occurred within the past month
21. Have uncontrolled hypertension (systolic BP above or equal to 160 mmHg and/or diastolic BP above or equal to 100 mmHg). If a participant is on anti-hypertensive therapies, doses must be stable for 30 days prior to screening. For participants with uncontrolled hypertension at the screening visit, antihypertensive medication may be started or adjusted. Blood pressure must meet the protocol criterion for hypertension control by Visit 3 with stable treatment for at least 30 days
22. Have an elevated resting pulse rate (>100 bpm) at baseline
23. Have any of the following cardiovascular conditions within 3 months prior to Screening:
- acute myocardial infarction
 - cerebrovascular accident (stroke)
 - unstable angina, or
 - hospitalization due to congestive heart failure (CHF)
24. Ongoing or history of frequent intermittent or chronic tachyarrhythmia syndromes (such as atrial fibrillation, supraventricular tachycardia, and positional orthostatic tachycardia syndrome).
- Note:** Participants with history of premature atrial contractions or premature ventricular contractions may be included.
25. Have NYHA Functional Classification III or IV CHF
26. Have an electrocardiogram (ECG) considered by the investigator indicative of active cardiac disease or with abnormalities that may interfere with the interpretation of changes in ECG intervals at screening
27. Have acute or chronic hepatitis, or signs and symptoms of any other liver disease other than NAFLD, or any of the following, as determined by the central laboratory during screening

- ALT level >3.0X upper limit of normal (ULN) for the reference range
 - alkaline phosphatase (ALP) level >1.5X ULN for the reference range, or
 - total bilirubin level (TBL) >1.5X ULN for the reference range (except for cases of known Gilbert's Syndrome)
28. Have a serum calcitonin level (at Visit 1) of
- ≥ 20 ng/L, if eGFR ≥ 60 mL/min/1.73 m² or
 - ≥ 35 ng/L if eGFR <60 mL/min/1.73 m² (as determined by central laboratory at Visit 1)
29. Have a family or personal history of medullary thyroid carcinoma (MTC) or multiple endocrine neoplasia (MEN) syndrome type 2
30. Have a history of an active or untreated malignancy or are in remission from a clinically significant malignancy (other than basal or squamous cell skin cancer, in situ carcinomas of the cervix, or in situ prostate cancer) for less than 5 years
31. Have any other condition not listed in this section (for example, hypersensitivity or intolerance) that is a contraindication to GLP-1RA
32. Have a history of any other condition (such as known drug or alcohol abuse, diagnosed eating disorder, or other psychiatric disorder) that, in the opinion of the investigator, may preclude the participant from following and completing the protocol
33. Alcohol consumption >14 units/week for women and >21 units/week for men
34. Have a history of use of marijuana or tetrahydrocannabinol (THC)-containing products within 3 months of enrollment or unwillingness to abstain from marijuana or THC-containing products use during the trial
- Note:* If a participant has used cannabidiol oil during the past 3 months but agrees to refrain from use for the duration of the study, the participant can be enrolled.
35. Have had a transplanted organ (corneal transplants [keratoplasty] are allowed) or are awaiting an organ transplant
36. Have any hematological condition that may interfere with HbA1c measurement (for example, hemolytic anemias and sickle cell disease)
37. Have had a blood donation of ≥ 500 mL within the previous 8 weeks of study screening or a blood transfusion or severe blood loss within the prior 3 months, or have known hemoglobinopathy, hemolytic anemia, sickle cell anemia, or have a hemoglobin value <11 g/dL (males) or <10 g/dL (females), or any other condition known to interfere with HbA1c methodology

38. Have a history of atopy (severe or multiple allergic manifestations) or clinically significant multiple or severe drug allergies, or intolerance to topical corticosteroids, or severe posttreatment hypersensitivity reactions (including, but not limited to, erythema multiforme major, linear immunoglobulin A dermatosis, toxic epidermal necrolysis, anaphylaxis, angioedema, or exfoliative dermatitis)
39. Have a fasting serum triglyceride level of >500 mg/dL at screening. If a participant is on lipid-lowering therapies, doses must be stable for 30 days prior to screening
40. Have evidence of a significant active, uncontrolled medical condition or a history of any medical problem capable of constituting a risk when taking the study medication or interfering with the interpretation of data, as judged by the screening investigator at screening
41. Have a history of symptomatic gallbladder disease within the past 2 years, defined by the presence of gallstones on an imaging study and abdominal pain attributed to the gallstones by the participant's physician; subjects who had a procedure to remove the gallstones and/or the gallbladder (cholecystectomy), with no long-term complications, are eligible for participation as long as the procedure was completed at least 3 months prior to screening
42. Have a history of documented human immunodeficiency virus (HIV) infection

Prior/Concomitant Therapy

43. Are receiving or have received within 3 months prior to screening chronic (>2 weeks) systemic glucocorticoid therapy (excluding topical, intraocular, intranasal, single intraarticular injection, or inhaled preparations) or have evidence of a significant, active autoimmune abnormality (for example, lupus or rheumatoid arthritis) that has required (within the last 3 months) or is likely to require, in the opinion of the investigator, concurrent treatment with systemic glucocorticoids (excluding topical, intraocular, intranasal, intraarticular, or inhaled preparations) during the course of the study
44. Have current treatment with or history of treatment with (within 3 months prior to screening) medications that may cause significant weight gain including, but not limited to, tricyclic antidepressants, atypical antipsychotics, and mood stabilizers

Examples:

- imipramine
- amitriptyline
- mirtazapine
- paroxetine
- phenelzine
- chlorpromazine
- thioridazine
- clozapine
- olanzapine
- valproic acid and its derivatives, and

- lithium.

Note: Selective serotonin reuptake inhibitors other than paroxetine are permitted.

45. Have taken within 3 months prior to screening medications (prescribed or over the counter) or alternative remedies intended to promote weight loss

Examples include, but are not limited to:

- Saxenda[®] (liraglutide 3.0 mg) or other GLP-1RA
- Xenical[®]/Alli[®] (orlistat)
- Meridia[®] (sibutramine)
- Acutrim[®] (phenylpropanolamine)
- Sanorex[®] (mazindol)
- Apidex[®] or Lomaira[™] (phentermine)
- Qsymia[™] (phentermine/topiramate combination)
- Contrave[®] (naltrexone/bupropion)

46. Use of metformin, or any other glucose-lowering medication, whether prescribed for polycystic ovarian syndrome or diabetes prevention is not permitted

47. Have started implantable or injectable contraceptives, such as Depo Provera[®] and Nexplanon[®], within 18 months prior to screening. Intrauterine devices, including levonorgestrel-releasing intrauterine systems, are allowed if the participant has been using the device for at least 3 months

Prior/Concurrent Clinical Study Experience

48. Have known allergies to GLP-1R agonists or LY3437943
49. Are currently enrolled in any other clinical study involving an investigational product (IP) or any other type of medical research judged not to be scientifically or medically compatible with this study
50. Within the last 30 days, have participated in a clinical study and received treatment, whether active or placebo. If the study involved an IP, 5 half-lives or 30 days, whichever is longer, should have passed
51. Have previously received LY3437943 as part of this study or any another study investigating LY3437943

Other Exclusions

58. Are investigator site personnel directly affiliated with this study and/or their immediate families. Immediate family is defined as a spouse, parent, child, or sibling, whether biological or legally adopted
59. Are Lilly employees

Note: The inclusion and exclusion criteria numbered from 52 to 57 are part of J1I-MC-GZBF Addendum (1). So, in Section 5.2, the exclusion criteria continue with the next available number in the sequence from the last number in the protocol addendum (58–59).

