	The C-SSRS, Self-Harm Supplement Form should be administered after assessment of adverse events. For this study, the C-SSRS is adapted for the assessment of the ideation and behavior categories only. The Intensity of Ideation and Lethality of Behavior sections are removed.																					
Columbia-Suicide Severity Rating Scale (C-SSRS) (Since Last Visit Version)			X	X	X	X	X	X	X	X	X	X	X	X	X	X	X	X	X	X	X	
Self-Harm Supplement Form	X		X	X	X	X	X	X	X	X	X	X	X	X	X	X	X	X	X	X	X	
Self-Harm Follow-up Form	X		X	X	X	X	X	X	X	X	X	X	X	X	X	X	X	X	X	X	X	
	Self-Harm Follow-up Form is only required if triggered by the Self-Harm Supplement Form, per instructions in the form.																					
Laboratory Tests and Sample Collections																						
Hematology	X			X			X	X			X			X			X		X		X	
HbA1c	X			X				X			X			X			X		X		X	
Urinalysis	X																					
Chemistry panel (includes creatinine for eGFR)	X			X			X	X			X			X			X		X		X	

	Study Period I Screening			Study Period II Treatment														99	ED	Study Period III Post- Treatment Safety Follow-Up		
	1	2	3	4	5	6	7	8	9	10	11	12	13	14	15	16	17			48	801	
Visit (see Notes below)	1	2	3	4	5	6	7	8	9	10	11	12	13	14	15	16	17	99	ED	801		
Week of Treatment	-6	-3	-1	0	1	4	8	12	16	20	24	28	32	36	40	44	48	48		4 Wks post end of TXP		
				Titration period																		
Allowable Interval Tolerance (days)	±7	±7	±7	-	±2	±3	±3	±3	±7	±7	±7	±7	±7	±7	±7	±7	±7	±7		±7		
Fasting Visit	X	X		X	X	X	X	X	X	X	X			X			X	X	X	X		
Telephone Visit												X	X		X	X						
calculation and glucose)	The CKD-EPI equation will be used by the central lab to estimate and report eGFR.																					
Lipid panel	X			X			X	X			X						X		X	X		
Longitudinal biomarkers				X			X	X			X						X		X			
	See Section 10.10 (Appendix 10) for list of biomarkers																					
Endpoint biomarkers				X							X						X		X			
	See Section 10.10 (Appendix 10) for list of biomarkers.																					
Serum pregnancy	X																					
	For women of childbearing potential only.																					
Urine pregnancy (local)				X				X			X			X			X		X			

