	
 Only for people identified with increased probability of liver fat ≥10% by liver fat algorithm from Visit 1. MRI will be performed after a fast of at least 6 hours. Participants can take necessary medications and small quantities of water during the fast. People who qualify for MRI based on the liver fat algorithm but have MRI contraindications may be enrolled in the main study but will not count towards the NAFLD subgroup population. Exceeding the window of assessment for MRI is not a protocol violation, but MRI results need to be available prior to Visit 3 (for more details, see Section 4.1.2.2). 																				
ABPM training			X																		
Initiate ABPM device			X							X				X							
	
 Participants are not allowed to perform strenuous activity on the day of the ABPM measurements. Participants should not be excluded from the study if arm circumference at Visit 3 does not allow for ABPM measurement. In those participants ABPM measurements should not be performed in the study. 																				
Return ABPM device and check validity of results			X							X				X							
	Participants should return the ABPM device at the conclusion of the 24- to 27-hour monitoring period.																				
Record ABPM measurements			X							X				X							
	At the time participant visit data is uploaded by the site, the ABPM Data Validity Report will be generated and should be reviewed to ensure ≥70% of the readings are valid. If <70% of the readings are valid, the 24-hour monitoring session should be repeated within the visit window (for more details, see Section 4.1.2.3).																				

Abbreviations: ABPM = ambulatory blood pressure monitoring; ADA = anti-drug antibody; BP = blood pressure; CKD-EPI = Chronic Kidney Disease-Epidemiology; ECG = electrocardiogram; ED = early discontinuation of treatment; eGFR = estimated glomerular filtration rate; HbA1c = hemoglobin A1c; IWRS= Interactive Web Response Systems; MRI = magnetic resonance imaging; NAFLD = non-alcoholic fatty liver disease; PK = pharmacokinetics; PR = pulse rate; SF-36v2 acute form = Short Form-36 Version 2 Health Survey acute form; TXP = treatment period.

General Notes:

- Telephone visits are shaded.
- Visit 4 baseline assessments must be completed before processing the randomization in the interactive web-response system (IWRS).

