6.5.1. Management of Participants with Gastrointestinal Symptoms

In the Phase 1 program, the most reported TEAEs for participants receiving LY3437943 were nausea, vomiting, and diarrhea. To mitigate GI symptoms and manage participants with intolerable GI AEs, the investigator should

- Advise participants to eat smaller meals, for example, splitting 3 daily meals into 4, or more smaller meals, and to stop eating when they feel full. Also, participants may be informed that lower-fat meals could be better tolerated.
- Prescribe symptomatic medication (for example, anti-emetic or antidiarrheal medication) per local country availability and individual participant needs. Use of symptomatic medication should be captured as concomitant medication in the eCRF.
- Temporarily interrupt study drug (omit 1 dose). Refer to Section 6.6.1 for further guidance on restarting study drug after temporary discontinuation of study drug. The data related to temporary interruption of study treatment should be documented in source documents and entered on the eCRF.

If intolerable GI symptoms or events persist despite the above measures, see Section 6.6.

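### Criterion 27 limits ALT, ALP and bilirubin at screening but not AST, so a participant can be randomised with AST already above a transaminase level used in Section 7.1

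*Protocol*

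**What the plan says.** Protocol 5.2, criterion 27, excludes clinical liver disease and three central-laboratory findings at screening: "ALT level >3.0X upper limit of normal (ULN) for the reference range", ALP above 1.5X ULN, and total bilirubin above 1.5X ULN (known Gilbert's syndrome excepted). AST is not mentioned there or in any other criterion of 5.1 or 5.2.

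AST is nevertheless measured. Appendix 2 (10.2) lists it under clinical chemistry, and the Schedule of Activities has the row "Chemistry panel (includes creatinine for eGFR" marked at Visit 1 and again at Visit 4.

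After randomisation the protocol treats the two enzymes together:

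- **Section 7.1** says discontinuation should be considered, after consulting the medical monitor, when ALT or AST is >8X ULN; >5X for more than 2 weeks; >3X with bilirubin >2X ULN or INR >1.5; or >3X with new symptoms that include nausea. One further condition is for ALT only: >2X baseline or ≥300 U/L, whichever comes first, if baseline ALT is ≥2X ULN.
- **Section 8.2.5.1** requires repeat tests within 48 to 72 hours when ALT or AST reaches ≥3X ULN (baseline <1.5X) or ≥2X baseline (baseline ≥1.5X).

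Other entry criteria bear on a raised AST only indirectly. The clinical clause of criterion 27 covers "signs and symptoms of any other liver disease other than NAFLD", so it exempts NAFLD. Criterion 32 rests on the investigator's opinion, and criterion 40 covers a problem "capable of constituting a risk when taking the study medication or interfering with the interpretation of data, as judged by the screening investigator". Criterion 33 excludes "Alcohol consumption >14 units/week for women and >21 units/week for men". The 5.2 note says "The inclusion and exclusion criteria numbered from 52 to 57 are part of" an addendum, which is not among the documents reviewed.

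**The concern.** An enzyme that can prompt consideration of stopping study drug has no numeric limit at entry, while its companion enzyme has one. Two consequences matter for participant safety.

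First, someone may start treatment with AST already above a 7.1 level. The symptom condition is the easiest to meet: Section 6.5.1 reports that in Phase 1 "the most reported TEAEs for participants receiving LY3437943 were nausea, vomiting, and diarrhea". A participant entering with AST >3X ULN meets that condition as soon as nausea appears, with no change in the liver test.

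Second, the repeat-test trigger for a raised baseline is a multiple of that baseline, while the >8X ULN level in 7.1 is fixed. With no upper limit on baseline AST, the trigger can lie above the level at which stopping is considered. The confirmatory test would then be required only after the decision it is meant to inform.

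The clinical clauses are a weak substitute. The study seeks about 100 to 125 participants with liver fat ≥10% (4.1, 5.1), and NAFLD is the liver condition that criterion 27 exempts.

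**Working it through.** The plan gives no figure of its own on this point. The check compares thresholds, all in multiples of ULN.

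**1. Limits side by side** (5.2, 8.2.5.1, 7.1)

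| Enzyme | Screening limit | Repeat-test trigger | 7.1 fixed levels | 7.1 baseline-relative level |
|---|---|---|---|---|
| ALT | >3.0X | ≥3X, or ≥2X baseline | >3X with bilirubin/INR or symptoms; >5X for over 2 weeks; >8X | >2X baseline or ≥300 U/L if baseline ≥2X |
| AST | none | same as ALT | same as ALT | none |

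**2. Entry above a 7.1 level.** With no AST limit, these screening values are admissible on the numeric criteria:

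- AST 3.5X: exceeds 3X, so the symptom condition is met once nausea appears.
- AST 5.5X: exceeds 5X, so the duration condition is met if the value is unchanged for more than 2 weeks.
- AST above 8X: the >8X condition is met at entry.

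ALT at its limit (3.0X) exceeds none of the fixed levels.

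**3. Repeat trigger against the >8X level.** For baseline b ≥ 1.5 the trigger is 2b, and 2b > 8 when b > 4.

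| Baseline AST | Trigger 2b | 8 − 2b |
|---|---|---|
| 3.0X | 6X | +2 |
| 3.5X | 7X | +1 |
| 4.0X | 8X | 0 |
| 4.5X | 9X | −1 |
| 5.0X | 10X | −2 |

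**4. Which row of 8.2.5.1 applies.** The rows are worded for ALT or AST jointly. If baseline ALT is also ≥1.5X, the 2X-baseline row clearly applies. If ALT is <1.5X, an enzyme-by-enzyme reading puts AST in the 2X-baseline row, but the wording also admits the first row, where AST ≥3X already triggers a repeat. The clear case needs ALT between 1.5X and 3.0X with AST above 4X. The AST multiple must then exceed the ALT multiple by a factor of more than 4/3.0 = 1.33 (ALT at 3.0X) to more than 4/1.5 = 2.67 (ALT at 1.5X).

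**5. Concurrent ALT.** In that clear case ALT triggers its own repeat at 2 × 1.5 = 3X to 2 × 3.0 = 6X, always below 8X. The late AST trigger matters only if AST passes 8X before ALT has doubled.

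**6. With AST capped at 3.0X at screening.**

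- No screening AST or ALT exceeds 3X, 5X or 8X.
- For a baseline at the cap, the repeat trigger is 2 × 3.0 = 6X, below 8X.
- Chemistry is drawn again at Visit 4, and "Visit 4 baseline assessments must be completed before processing the randomization". The cap does not bind that value. It would have to be more than 4.0/3.0 − 1 = 33% above a screening value of 3.0X for the trigger to pass 8X again.
- Against the >5X-for-2-weeks level, 2b > 5 when b > 2.5. Baselines from 2.5X to 3.0X, for either enzyme, still have a trigger above 5X.
- Comprehensive evaluation without symptoms starts at 3 × 3.0 = 9X for a baseline at the cap, still above 8X.

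**7. Frequency.** None is given. Purely as an assumption, 0% to 1% of 300 randomised is 0 to 3 participants.

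**The case against.** The strongest reply is that the mis-ordering comes from setting baseline-relative triggers in 8.2.5.1 against fixed levels in 7.1, and that criterion 27 is not its source. ALT shows this. With baseline ALT 3.0X, the ALT-only condition considers stopping above 6X, and the repeat trigger is also 6X, so there is no real margin. If the ALT ULN exceeded 300/6 = 50 U/L (an assumption; the documents give no ULN), the 300 U/L limb would come before the repeat. This stands. A reader might infer that capping AST restores an early-warning margin of 2X ULN like the one ALT has. The documents do not support that, because ALT does not have one.

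It also stands that the cap leaves the >5X ordering in place for baselines above 2.5X, that a doubling of ALT can trigger the repeat first, and that 8.2.4 separately has the investigator review results and repeat clinically significant abnormal tests. A reader might infer that repeat testing of a high AST is unavailable until 2X baseline; 8.2.4 contradicts that.

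Finally, the symptom condition leads to a consultation, and an ALT of 3.0X needs only a slight rise to meet it too. That limits the harm from meeting it early.

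None of this answers the central point: the numeric criteria allow enrolment with AST above a 7.1 level, and neither document gives a reason for limiting ALT alone.

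**Conclusion.** The concern holds as a minor gap in eligibility. Nothing numeric in 5.1 or 5.2 stops a participant being randomised with AST above 3X, 5X or even 8X ULN. Prevention rests on judgement under criteria 27, 32 and 40, with the alcohol limit acting only indirectly. Above a baseline of 4X, where the ≥1.5X row applies, the AST repeat trigger also passes the >8X level, subject to the ALT and 8.2.4 routes.

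It would be wrong to read this as absent hepatic protection. The fixed levels in 7.1 apply whatever the baseline, and they call for consideration after consultation, not an automatic stop. No effect on an efficacy endpoint or analysis is claimed.

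The number affected is probably small but unknown; the 0 to 3 above is an assumption. Addendum criteria 52 to 57 could contain an AST limit for the liver-fat subgroup. That cannot be checked, and such a limit would not cover the rest of the study.

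**What to change.** Change the first bullet of criterion 27 so that the 3.0X ULN limit applies to ALT or AST. No screening value of either enzyme could then exceed any fixed transaminase level in 7.1. No change to 7.1 or the SAP is proposed for this purpose.

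The amendment should not be presented as guaranteeing the Visit 4 baseline or as resolving the >5X ordering.

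The cost is one phrase in a protocol amendment, which needs IRB/IEC approval under 10.1.1, and a few more screen failures. No new test is needed, because AST is already drawn at Visit 1. The change does nothing for participants already randomised.
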